Thermoregulation and Cognition During Cool Ambient Exposure in Tetraplegia

NCT02379156

Most Recent Update / Human Subjects Protection Review Board Approval: 03/07/2023

RESEARCH PROTOCOL

1. SPECIFIC AIMS.

Problem Statement: After a cervical spinal cord injury (SCI) the motor, sensory and autonomic deficits cause, among other detriments, a blunted ability to maintain a constant core body temperature (Tcore). Impaired thermoregulation leaves persons with tetraplegia more susceptible to hypothermia than able-bodied persons (AB). In addition, the commonly prescribed medications to treat the spasticity, pain, and depression that accompany this injury, raise the vulnerability of this population to hypothermia, and its potentially fatal consequences.

Persons with tetraplegia are routinely exposed to cool ambient temperatures in their homes, work environments, and while waiting on or riding in accessible public transportation. The thermoregulatory response and cognitive consequences of prolonged exposure to cool temperatures have not been investigated in persons with tetraplegia. Preliminary data has suggested that even limited exposure to cool temperatures can cause a drift in Tcore to values approaching hypothermia. With this lowering of Tcore, cognitive performance may also be negatively affected. Such demonstration of mild (or worse) hypothermia and concomitant declines in cognitive function would warrant investigations of interventions to mitigate this drift in persons with tetraplegia. The International Spinal Cord Injury Skin and Thermoregulation Basic Data Set is further evidence of the growing recognition that many people with SCI are affected by thermoregulatory dysfunction.

There has been a paucity of work addressing the thermoregulatory responses of persons with SCI to cool ambient temperatures, and even less study of medical interventions to improve maintenance of Tcore. Although it is presently unknown as to whether a modest fall in Tcore impairs cognition in persons with SCI, one may expect deterioration in cognitive function because central neurological function is exquisitely temperature sensitive. As such, cognitive performance will be determined after decrement in core body temperature.

The goals of this study are: 1) to improve our understanding of the thermoregulatory mechanisms of individuals with tetraplegia when exposed to cold, 2) to determine if cognitive performance is affected after a decrement in Tcore, and 3) to determine if administration of an alpha-adrenergic agonist (midodrine) delays or decreases the expected downward drift in Tcore and possible deterioration of cognitive performance.

In order to address our goals, we have designed a study methodology which consists of comparing the physiological and subjective responses of the two study groups (tetraplegia versus AB controls) from thermoneutral (27°C) to cool (18°C) environments in the seated position. On a 2nd visit, the subjects with tetraplegia who completed the first visit, will be given midodrine while seated prior to being placed in the cool environment to compare their responses with midodrine to their responses to the identical challenge without midodrine.

Overall Objective: The overall objective is to identify and address the physiological and cognitive problems that persons with spinal cord injury (SCI) face when exposed to routinely encountered cool temperatures.

- Specific Aims: during exposure to a cool environment (18°C) for up to 120 min in the seated position:

Primary Specific Aim: To determine the change in: (1) Tcore and to assess (2) cognitive performance (attention, processing speed, working memory, and executive function) before and

after exposure to cool temperatures. **Primary Hypotheses:** Based on our pilot data: (1) Sixty-six percent of persons with tetraplegia and none of the controls will demonstrate a decline of 1.0°C in Tcore; (2) Eighty percent of persons with tetraplegia and 30% of controls will have a decline of at least one T-score in Stroop Interference scores (a measure of executive function).

Secondary Specific Aims: To determine the change in: (1) the average of distal skin temperatures, (2) metabolic rate, and (3) subjective rating of thermal sensitivity. **Secondary Hypotheses:** Persons with tetraplegia will have less of a percent change in average distal skin temperatures and metabolic rate, and report blunted thermal sensitivity ratings compared with able-bodied (AB) controls.

Tertiary Specific Aim: To determine if a 10 mg dose of midodrine will (1) reduce the decrease in Tcore and (2) prevent or delay the decline in cognitive performance in the group with tetraplegia.

Tertiary Hypothesis: Because the one-time, off-label use of midodrine will address the primary systemic impairment to cold exposure in persons with tetraplegia, lack of peripheral vasoconstriction, the induced vasoconstriction will serve to reduce cutaneous heat losses and will be anticipated to blunt the decrease in Tcore and delay the decline in cognitive performance compared to cool exposure without drug administration.

METHODS

Research Design and Methods: A prospective, two-group comparative study will be performed to determine the effects of cold thermal challenge on Tcore, cognitive performance, distal skin temperatures (Tsk), metabolic rate (VO₂), and thermal sensitivity (TS) in the seated position in individuals with tetraplegia and in a matched AB control group (Visit 1). During Visit 2, a prospective, within-group comparative study will be performed to determine the effects of cold thermal challenge on Tcore, cognitive performance, Tsk, VO₂, and TS only in individuals with tetraplegia after midodrine administration compared to their response on Visit 1.

A prospective, two-group comparative study will be performed to determine the effects of cold thermal challenges on core temperature measured by rectal thermocouple (Tre), skin temperature by surface thermocouples (Tsk), cognitive performance by [digit span section of the Wechsler Adult Intelligence Scale-Fourth Edition (WAIS-IV), Stroop Color and Word tests, Symbol Digit Modalities Test (SDMT), memory and delayed recall sections of the Montreal Cognitive Assessment (MoCA)], metabolic rate measured by oxygen consumption (VO₂), and thermal sensation by the thermosensitivity cold scale in the seated position in individuals with tetraplegia and in a matched AB control group (Visit 1). During Visit 2 a prospective, within-group comparative study will be performed to determine the effects of thermal challenge on Tcore, skin temperature, cognitive performance, metabolic rate, and thermal sensation in individuals with tetraplegia who have participated in Visit 1 and in those same individuals who repeat the Visit 1 challenge identically, except for the administration of midodrine prior to the cold challenge while in the seated position (Visit 2).

Subjects: Fifteen subjects with tetraplegia (C4-T1) and 15 non-SCI control subjects matched for age (\pm 5 years), and gender will be recruited for study.

Subject Recruitment:

Patients referred by their physician following routine physical examinations will be approached for possible study enrollment. Physicians will be informed of the inclusion and exclusion criteria for this study and will be able to provide us with the assurance that the patient is an appropriate study subject and that they were willing to speak with the study coordinators.

Veterans with SCI responding to IRB approved articles in lay publications and advertisements. Veterans with an ongoing relationship with our center, such as through attendance at one of the following SCI clinics: (1) Metabolic, (2) Pulmonary, or (3) GI.

a. Inclusion criteria

1. Between 18 and 68 years of age;
2. Duration of injury \geq 1 year;
3. Level of SCI C4-T1; (AIS A & B)
4. Euhydration (Subjects will be instructed to avoid caffeine and alcohol, maintain normal salt and water intake, and avoid strenuous exercise for 24 hours prior to study); and
5. Age (\pm 5 years) and gender matched AB control group.

b. Exclusion criteria

1. Evidence of sympathetic integrity below the lesion level by the skin axon-reflex vasodilatation (SkARV) test (a distinctly diminished vasodilatory response to mechanical stimulation of the skin is evident below the lesion level when sympathetic integrity has been interrupted);
2. Known allergies to midodrine hydrochloride;

Exclusion Criteria shared by subjects with SCI and AB controls

3. PMH of diagnosed heart, kidney, peripheral vascular, or cerebral vascular disease, or diabetes mellitus;
4. Hypertension (BP>140/90 mmHg);
5. Untreated thyroid disease;
6. Acute illness or infection;
7. Current smoker;
8. Pregnancy.

Preparation for Study Visits: AB controls will be gender- and age-matched (\pm 5 years) to subjects with SCI. All subjects will be instructed to avoid caffeine and alcohol, maintain normal salt and water intake, and avoid strenuous exercise for 24 hours prior to study to ensure euhydration. Subjects will enter the laboratory between 8:00-10:00 AM on each study visit. Study visits will be separated by a minimum of 1 day and no more than 14 days. Subjects will wear minimal clothing (gym shorts, sports bra) during the study to maximize skin exposure to the cool temperature. Each subject will be asked to eat a light, standard meal (plain bagel or 2 pieces of toast) 2 hours prior to their visit. Subjects will be asked to empty their bladders prior to each study visit and again upon arrival, if needed.

Visit 1: Cool Ambient Challenge: Instrumentation: During Visit 1, all subjects will be instrumented on a padded table, after which they will be transferred back to their wheelchair or, for controls, to a provided wheelchair. All subjects will use a Roho seat cushion (high-profile single compartment ROHO seat cushion, the Roho Group, Belleville, IL) for air circulation consistency and decubiti prevention. A rectal probe will be placed 10 cm beyond the anal sphincter for core temperature collection, and skin thermocouples will be secured at 15 sites above and below the level of lesion for collection of skin temperatures. A dilution mask will be placed over the subject's nose and mouth for collection of exhaled gases from which resting metabolic rate will be calculated from analysis of expired gases (VO_2) by a metabolic cart. Laser Doppler flowmetry (LDF) will be used to measure changes in microvascular perfusion by placing a doppler probe on the skin in the area of the ulnar styloid processes and medial malleoli bilaterally (wrists and ankles) to confirm vasoconstriction. A pulse oximeter will be placed on the second digit to obtain blood oxygen saturation and heart rate (HR). A BP cuff will be placed above the right elbow to measure brachial BP. An intravenous catheter will be placed in an upper extremity vein for sequential blood draws to assess plasma NE and cortisol levels.

Baseline Collection: At the end of the 30-minute acclimation period (27°C), a baseline (BL) collection of the following parameters will be performed for 15 minutes with Tcore, Tsk, and VO₂ measured continuously; HR, BP, blood oxygen saturation, subjective measures of TS, and 5 minutes of LDF will be measured at 10-minute intervals. A venous blood draw will be collected once at baseline for NE and cortisol concentrations. At the end of the BL period, hypertonicity (spasticity) will be measured only in subjects with tetraplegia in both upper extremities, at the elbows and wrists (flexors and extensors) and both lower extremities, at the knees and ankles (flexors and extensors) using the Modified Ashworth Scale. Once the spasticity measurement is completed, a cognitive performance battery will be administered.

Thermal Challenge: Following completion of the BL period, subjects will be wheeled into an 18°C thermal chamber for 120 minutes or until Tcore ≤ 35°C. Tcore, Tsk, and VO₂ will be continuously monitored to ensure subject safety throughout the protocol; brachial BP, HR, blood oxygen saturation, TS, and symptoms of autonomic dysreflexia and hypothermia will be assessed at 10-minute intervals while LDF will be measured for 5 minutes every 20 minutes. Venous blood will be collected at 50-minute intervals. After 1 hour of Cold Challenge, hypertonicity (spasticity) will be measured again only in subjects with tetraplegia in both upper extremities, at the elbows and wrists (flexors and extensors) and both lower extremities, at the knees and ankles (flexors and extensors) using the Modified Ashworth Scale. A decrease in Tcore to ≤ 35°C, or subject discomfort, will result in termination of the protocol. The cognitive performance battery will be administered when Tcore has declined 1°C or is ≤ 35.5°C (in subjects with tetraplegia) or after 120 minutes of cold exposure (in both groups) on Visits 1 & 2.

Visit 2: Cold Ambient Challenge with Midodrine: Visit 2 will be completed in subjects with tetraplegia who participated in Visit 1 and who had an impaired ability to maintain Tcore. Following completion of the BL period, hypertonicity (spasticity) will be measured only in subjects with tetraplegia in both upper extremities, at the elbows and wrists (flexors and extensors) and both lower extremities, at the knees and ankles (flexors and extensors) using the Modified Ashworth Scale. Subjects will then be orally administered midodrine hydrochloride (10 mg). Forty minutes after midodrine administration (for onset of drug effect), a second BL collection will be obtained, and hypertonicity (spasticity) will again be measured only in subjects with tetraplegia in both upper and lower extremities. Subjects will then be wheeled into the 18°C thermal chamber for 120 minutes or until Tcore ≤ 35°C. Data collection will follow the same schedule and be conducted in the seated position as in Visit 1. After 1 hour of Cold Challenge, hypertonicity (spasticity) will again be measured in both upper and lower extremities.

Statistical Analyses: *Visit 1:* Depending on the data distribution, parametric or non-parametric analyses will be performed. For the within-group comparisons, paired-t and Wilcoxon signed rank tests will be conducted to determine intra-group differences in the dependent variables. For the between-group comparisons, unpaired-t and Mann-Whitney U tests will be performed to determine between-group differences in the percentage change (from thermoneutral to cool) of the dependent variables (Tcore, cognitive performance, Tsk, and VO₂).

Visit 2 (with midodrine): Depending on the data distribution, parametric or non-parametric analyses will be performed. Within the group with tetraplegia, paired-t or Wilcoxon signed rank tests will be used to determine differences in the percentage change (from thermoneutral to cool) of the dependent variables (Tcore, cognitive performance, Tsk, VO₂), without midodrine (Visit 1) compared to with midodrine (Visit 2).

Sample size: The primary outcome variables are Tcore and cognitive performance. For Tcore, using our preliminary data obtained post cold exposure in tetraplegic and AB subjects, mean Tcores of $35.95 \pm 0.63^\circ\text{C}$ and $37.3 \pm 0.28^\circ\text{C}$ were demonstrated, respectively. The difference between the groups for these values yields a power of 99.9% at an alpha of 0.05 with 8 subjects

per group (double-sided). Four of the 6 subjects with tetraplegia (66%) had a decrease of $\geq 1.0^{\circ}\text{C}$ while no control demonstrated a decline $> 0.297^{\circ}\text{C}$ in Tcore (0%). Cognitive performance will be assessed after a Tcore decline of 1.0°C in subjects with tetraplegia. Using 66% (tetraplegia) versus 0% (control) with a count of 15 per group, the power is 99.59% at an alpha of 0.05. We are hypothesizing that 66% of subjects in the SCI group will have a decline of 1.0°C in Tcore while none of the controls will demonstrate the same decline. We are well-powered to test this endpoint. For cognitive performance, preliminary data indicated that 5 of 6 subjects with tetraplegia (83%), compared to 2 of 6 AB subjects (33%), demonstrated a decline of ≥ 1 T-score in Stroop Interference scores post cold exposure. Using 83% (tetraplegia) versus 33% (control) with a count of 15 per group, the power is 82.75% at an alpha of 0.05 (double-sided).⁷⁶ We hypothesize that 80% of subjects in the SCI group will have a decline of at least 1 T-score in Stroop Interference scores while 30% of controls will demonstrate that same decline. We are well-powered to test this outcome.

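### The primary cognitive hypothesis and its power count any fall of 1 T-score (0.1 SD) as a decline, a cut the plan does not justify and a quantity the planned analysis does not test

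*Combined protocol and SAP*

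**What the plan says.** Under Specific Aims, Primary Hypotheses, the second hypothesis concerns the share of subjects who "will have a decline of at least one T-score in Stroop Interference scores (a measure of executive function"). The expected rates are 80% with tetraplegia and 30% among controls.

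The Sample size section repeats it: "We hypothesize that 80% of subjects in the SCI group will have a decline of at least 1 T-score in Stroop Interference scores", against 30% of controls. The rates come from a pilot with six subjects per group, in which 5 with tetraplegia and 2 controls met the definition. The calculation is introduced by "Using 83% (tetraplegia) versus 33% (control) with a count of 15 per group" and concludes that "the power is 82.75% at an alpha of 0.05 (double-sided").

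On Visit 1 the cognitive battery is given once at the end of baseline and once in or after the cold (Baseline Collection; Thermal Challenge). Each subject is therefore classified from a single difference between two scores.

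Statistical Analyses, Visit 1, compares the groups on percentage change from thermoneutral to cool, using unpaired t or Mann-Whitney tests, and lists cognitive performance among the variables. It names no test of the proportion of decliners.

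**The concern.** A T-score is scaled to SD 10, so the cut is 0.1 SD. With one test and one retest, ordinary measurement error in the difference is likely to be several points. The count would then record little more than whether the second score was lower. A statement that 80% declined would say little about how many people had executive function impaired by cooling.

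Two further things are at stake. Reducing a continuous score to yes or no discards information, which matters with 15 per group. And the hypothesis and its power concern proportions while the analysis compares percentage change, so the claim of adequate power does not attach to the test that will be run.

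**Working it through.** **1. The plan's own power.** Inputs from Sample size: p1 = 0.83, p2 = 0.33, n = 15 per group, two-sided alpha 0.05. Pooled-variance normal formula, with p̄ = 0.58:

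z = [(p1 − p2)√n − 1.96·√(2p̄(1 − p̄))] / √(p1(1 − p1) + p2(1 − p2)) = [0.50 × 3.873 − 1.96 × 0.698] / 0.602 = 0.945

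Power = Φ(0.945) = 82.75%, as stated. At the hypothesised 80% versus 30% the same formula gives 82.0%. The arithmetic is sound, but it is power for comparing two proportions.

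**2. Decliners when nothing has changed.** Inputs: cut of 1 point (Primary Hypotheses); SD 10 (definition of a T-score); retest correlation r and practice gain g, neither in the plan, both assumed. With normal changes:

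SD of change = 10√(2(1 − r)); P(fall ≥ 1) = Φ((−1 − g) / SD of change)

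| r | SD of change | g = 0 | g = 1 | g = 2 |
|---|---|---|---|---|
| 0.5 | 10.0 | 46.0% | 42.1% | 38.2% |
| 0.7 | 7.75 | 44.9% | 39.8% | 34.9% |
| 0.8 | 6.32 | 43.7% | 37.6% | 31.8% |
| 0.9 | 4.47 | 41.2% | 32.7% | 25.1% |
| 0.95 | 3.16 | 37.6% | 26.4% | 17.1% |
| 0.98 | 2.00 | 30.9% | 15.9% | 6.7% |

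With g = 0 the rate passes 40% only if the SD of change exceeds 3.95 points, that is r below about 0.92. If scores are recorded in whole points (effective cut −0.5), the 41.2% at r = 0.9 becomes 45.5%.

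**3. What 80% would need.** Under the same model the mean fall giving 80% decliners is 1 + 0.842 × SD of change: 4.8 points at r = 0.9 and 9.4 at r = 0.5.

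**4. How firm the control rate is.** Pilot controls: 2 of 6, exact 95% CI 4% to 78%. If the control rate were 40% to 45% with tetraplegia at 80%, the formula in step 1 gives power of 62% to 51% at 15 per group, and 80% power would need 23 to 29 per group.

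**5. Power for mean change.** If 80% and 30% arise from normal changes with equal SD, the group means differ by z(0.80) − z(0.30) = 0.842 + 0.524 = 1.366 SDs of change, whatever r is. Noncentrality = 1.366 × √(15/2) = 3.74. A two-sided t test on 28 df then has power of about 95%, against 82.0% for the yes/no count.

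**6. Points or percentage.** The T-score's centre of 50 is a convention, so percentage change depends on the starting score. A 5-point fall is 12.5% from 40 (5/40) but 8.3% from 60 (5/60).

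**The case against.** The strongest reply is that the hypothesis is comparative. Chance declines fall in both groups, so they do not by themselves produce a false difference. The plan speaks of a decline, never of impairment, and it already intends to compare change between groups by t or Mann-Whitney test, so much of the remedy is in place. All of that stands. What remains is the percentage scale, the absence of an interval estimate, and a hypothesis and power figure stated for something else.

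A reader might also infer more than the documents support:

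- *That over 40% of unchanged subjects would be counted, whatever the assumptions.* This does not follow from the 0.1 SD ratio. It also needs r below about 0.92 and almost no practice gain: gains of about 1.0, 0.6 or 0.1 points at r = 0.7, 0.8 or 0.9 bring the rate down to 40%. A sample SD below 10 also lowers it; at SD 7, r = 0.85 to 0.9 gives 40% to 37%.
- *That the expected result is mostly noise.* Step 3 shows otherwise: noise around zero change cannot give 80%.
- *That the pilot controls prove the point.* Two of six confirms no particular rate, and the controls also sat in the cold.
- *That the contrast is a practice artefact.* A gain shared by both groups cancels in the difference of mean changes. Only a group-specific gain would matter. The second battery can come earlier in tetraplegia, once core temperature has fallen, than in controls, so the intervals may differ, but nothing in the plan shows or sizes such a gain.

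**Conclusion.** The concern holds for the hypothesis and the sample-size justification. The 1-point cut is unjustified and lies well inside plausible retest error: 41% to 46% of unchanged subjects would be counted for r from 0.9 down to 0.5 with no gain, or 33% to 42% with a 1-point gain. Even at r = 0.98 with no gain the figure is 31%. These figures rest on normal changes, SD 10 and an assumed r, because the plan supplies no reliability data. The consequences are limited interpretability of the decliner share, lost information, and a power figure that does not belong to the planned test. Inflated type I error is not among them.

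**What to change.** State the primary cognitive endpoint as the between-group difference in mean Stroop Interference T-score change, in points and not percentage, with a 95% CI. Replace the 82.75% with power for that endpoint, about 95% at 15 per group on the assumptions in step 5, and state those assumptions. Keep the 1-point count, if wanted, as descriptive only, labelled *any lower score*.

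This needs no new data and no extra subjects; the cost is rewording the hypothesis, analysis and sample-size text. The replacement power still leans on pilot rates from six subjects per group. A reliable-change limit from the trial's own controls (control mean change minus 1.645 × control SD of change) could be added to describe individuals, but with 15 controls it would be imprecise and is optional.

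### The Visit 1 versus Visit 2 comparison cannot attribute a difference to midodrine, because drug and visit coincide and entry to Visit 2 depends on the Visit 1 result that then serves as comparator

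*Combined protocol and SAP*

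**What the plan says.** Specific Aims poses a causal tertiary question: does a single dose of midodrine lessen the fall in core temperature (Tcore) and prevent or delay cognitive decline in the tetraplegia group?

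The design behind it is set out in four places.

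- **Order and comparator.** Drug is given at the second visit only: "On a 2nd visit, the subjects with tetraplegia who completed the first visit, will be given midodrine while seated" (Specific Aims). The comparison is made "only in individuals with tetraplegia after midodrine administration compared to their response on Visit 1" (Research Design and Methods). The same section says the second session is identical to the first "except for the administration of midodrine prior to the cold challenge while in the seated position".
- **Who enters.** The section describing the midodrine session sets a condition: "Visit 2 will be completed in subjects with tetraplegia who participated in Visit 1 and who had an impaired ability to maintain Tcore". Specific Aims and Research Design and Methods describe entry by completion of, or participation in, Visit 1, with no condition on the result.
- **Procedure at Visit 2.** "Forty minutes after midodrine administration (for onset of drug effect), a second BL collection will be obtained". No such wait or second baseline is described for Visit 1. Under Preparation for Study Visits: "Study visits will be separated by a minimum of 1 day and no more than 14 days".
- **Analysis.** Under Statistical Analyses, "paired-t or Wilcoxon signed rank tests will be used to determine differences in the percentage change (from thermoneutral to cool" for each dependent variable, with Visit 1 (no drug) set against Visit 2 (drug).

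The document mentions no placebo, blinding, randomised or balanced order, repeat drug-free visit, or period term. Controls have no second visit.

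**The concern.** In the paired test, visit number and drug are the same variable. Whatever changes a subject's response between the two sessions enters the estimate labelled as midodrine, and no analysis of these data can take it out. Three sources can be identified from the document:

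1. **Regression to the mean.** If only subjects with a poor Visit 1 result go on, and that result is the comparator, their Visit 2 fall in Tcore is expected to be smaller even with an inert tablet. For Tcore this favours midodrine.
2. **Unequal procedures.** Visit 2 has a longer pre-exposure period and two baselines. The plan does not say which baseline enters the percentage change.
3. **A visit effect on the change itself.** Examples are habituation to the cold, or a practice gain between the two cognitive batteries that differs from one visit to the other.

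At stake is the tertiary conclusion only. The Visit 1 comparison of tetraplegia with controls is untouched.

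**Working it through.** **The plan's own figures.** No power or sample size is stated for the Visit 2 comparison. The Visit 1 rate figures under Sample size reproduce with the pooled two-proportion formula, power = Φ{[|p1−p2| − 1.96√(2p̄(1−p̄)/n)] / √([p1(1−p1)+p2(1−p2)]/n)}, n = 15 per group:

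- 66% v 0%: (0.66 − 1.96 × 0.1717)/0.1223 = 2.64, power 99.59% (stated 99.59%).
- 83% v 33%: (0.50 − 1.96 × 0.1802)/0.1554 = 0.944, power 82.75% (stated 82.75%).

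They say nothing about the midodrine contrast.

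**Inputs for Visit 2.** From the document: 15 subjects with tetraplegia, 66% expected to fall by 1.0°C, and a paired test. Two-sided 5% is assumed for Visit 2. Also assumed: that the 66% approximates the share entering Visit 2 (0.66 × 15 = 9.9, about 10), since the entry condition is not defined numerically; the size of any visit effect; and the between-visit correlation. The document gives neither of the last two, nor a within-subject SD.

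**Check 1: net visit effect, no drug effect, no selection.** Let δ be the visit effect on the difference in percentage change, divided by the SD of the paired difference. The chance of a significant result favouring midodrine is P{T > t(0.975, n−1)}, where T is noncentral t with n−1 degrees of freedom and noncentrality δ√n. Critical values are 2.262 (n = 10) and 2.145 (n = 15).

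| δ (assumed) | n = 10 | n = 15 |
|---|---|---|
| −0.3 | 0.2% | 0.1% |
| 0 | 2.5% | 2.5% |
| 0.2 | 8% | 11% |
| 0.3 | 13% | 19% |
| 0.5 | 29% | 44% |

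For example, δ = 0.5 gives noncentrality 0.5 × √10 = 1.58, hence 29%, and 0.5 × √15 = 1.94, hence 44%.

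**Check 2: selection on Visit 1, no drug effect, no visit effect.** Simulate the fall in Tcore at each visit for 15 subjects as bivariate normal with equal variances and correlation r. Keep the 10 with the largest Visit 1 fall and apply the paired t test.

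| r (assumed) | Significant, favouring midodrine |
|---|---|
| 0.9 | 5% |
| 0.7 | 9% |
| 0.5 | 13% |

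The nominal rate is 2.5%. The size of the artefact follows from the truncated normal. With the upper two-thirds selected, the mean Visit 1 excess is φ(z)/(2/3) = 0.545 SD, of which a fraction 1 − r is lost at Visit 2. Taking 0.63°C as the SD of the fall (the document gives it for post-exposure Tcore, so this is a stand-in), the apparent benefit is 0.545 × 0.63 × (1 − r) = 0.03, 0.10 and 0.17°C at r = 0.9, 0.7 and 0.5.

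**Check 3: are the visits identical apart from drug?** Research Design and Methods says yes. The Visit 2 section adds the 40-minute wait, a second baseline and a further spasticity assessment before the cold exposure. The two descriptions do not agree.

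**The case against.** The strongest reply has four parts.

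- **The outcome is change within a visit.** A reader might infer that every order, habituation or practice effect is counted as drug effect. The analysis plan does not support that: an effect shifting baseline and cold values alike at Visit 2 largely cancels from the percentage change. Only an effect on the change itself remains. This stands, and the δ in Check 1 must be read as that net quantity.
- **Practice has no fixed direction.** A reader might infer that repeated cognitive testing must flatter midodrine. If the practice gain is largest between the first and second batteries, both at Visit 1, it hides decline there and works against the drug. The document also does not explicitly list a baseline battery at Visit 2. This stands too; a bias of unknown sign nevertheless still prevents attribution.
- **Core temperature is a thermocouple reading under standardised conditions.** Test practice is irrelevant to it; arrival time, meal, clothing and prior exercise are controlled; habituation after one exposure of at most 120 minutes is not documented. This weakens the habituation argument, but it answers neither regression to the mean nor the longer pre-exposure period.
- **This is a tertiary, openly described within-group comparison with no power claim.** True, and it limits the seriousness. But the aim and hypothesis are worded causally, and that wording is what the design cannot support.

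Regression to the mean also depends on which entry rule applies. If all who complete Visit 1 proceed, as Specific Aims can be read, Check 2 falls away and only the visit effect and unequal procedures remain.

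**Conclusion.** The point holds for the tertiary aim. The contrast "without midodrine (Visit 1) compared to with midodrine (Visit 2" confounds drug with visit, and the design contains nothing that could separate them.

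The best-grounded threats come from the document itself: entry conditioned on the result later used as comparator, and a Visit 2 procedure that differs by more than the drug. Selection alone raises the chance of a falsely favourable Tcore result from 2.5% to between 5% and 13%, for assumed correlations of 0.9 down to 0.5 and 10 of 15 entering. An assumed net visit effect of 0 to 0.5 SD would give 2.5% to 29% with 10 subjects, or 2.5% to 44% with 15; a negative one takes it below 2.5%. These are illustrations, not estimates. The document does not show that a visit effect of any particular size or sign exists, and the conclusion does not need one: it rests on the confounding.

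Nothing here bears on the primary or secondary Visit 1 comparisons or on their stated power.

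**What to change.** 1. Restate the tertiary aim, the tertiary hypothesis and the Visit 2 analysis as an exploratory, uncontrolled before-after comparison. Do not attribute the Visit 1 to Visit 2 difference to midodrine, and name regression to the mean, visit order and the longer pre-exposure period as alternative explanations.
2. Reconcile Specific Aims and Research Design and Methods with the Visit 2 section on who enters Visit 2. Which rule applies is for the investigators; the analysis needs one stated rule.
3. Reconcile the statement that the visits are identical apart from drug with the Visit 2 procedure, and say which Visit 2 baseline enters the percentage change.

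The cost is a weaker tertiary claim and some redrafting, with no new subjects or sessions. Randomising session order is an option for a future study, not a required change here. It would make about half of the tetraplegia group's drug-free sessions second sessions while every control session stays a first, altering the primary comparison to serve a tertiary aim.
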